## 3 Protocol Summary

**Protocol Title:** A Phase 2 randomised, single blinded, placebo controlled, cross-over trial of a single dose of live attenuated influenza vaccine in 12-23 month old children (FluSNIFF Toddler).

**Rationale:** This study will collect and analyse data on the safety of giving a single dose of live attenuated influenza vaccine (LAIV) to young children aged 12-23 months inclusive. The primary outcome is medically attended wheeze in the first 28 days following vaccine administration.

For this study, wheeze will be defined as a physician-diagnosed wheeze or asthma (practice, home visit or hospital) or an illness for which the child was prescribed medication used to treat wheeze or asthma.

### **Objectives and endpoints:**

Outcomes		
Primary		
Incidence of medically attended, physician- diagnosed wheeze or asthma or an illness for which the child was prescribed asthma medication.		
Secondary		
All medically attended adverse events		

**Brief Summary:** This study is a blinded, cross-over, randomised controlled trial of LAIV compared to placebo nasal spray in children aged 12 to 23 months. The primary outcome is medically attended wheeze in the four weeks following vaccination. To reduce the burden on GPs, study outcomes will be assessed by remote data extraction from electronic health records.

[figure not shown]
There will be two in-person study visits and one visit by digital questionnaire. At the first visit, participants will be consented, screened and randomised 1:1 to receive either LAIV or placebo nasal spray. Four weeks later at the second visit, basic safety information will be collected, and the participants will receive either vaccine or placebo (whichever they did not receive at the first visit). The final visit will be four weeks later and will be conducted via digital questionnaire to collect safety information. Recruitment will be enriched for children with a history suggestive of increased risk of wheezing, including a personal history in the child of eczema, bronchiolitis or viral induced wheeze.

**Number of Participants:** A total of 3000 children are expected to be randomised.

Interventions: All participants will receive live attenuated influenza vaccine (LAIV) (Fluenz, AstraZeneca) during the study. This is a live, attenuated, cold adapted influenza vaccine which is delivered as a nasal spray as 0.1ml solution per nostril. Participants will be randomised to either receive this at the first or second study visit. When not receiving LAIV they will receive 0.1ml per nostril of placebo, administered as normal saline via 1ml syringe and nasal atomiser device. Parents will be blinded to allocation.

### Study flow diagram

#### **Abbreviated Schedule of visitations**

	Early Vaco	ine Group	
	D0	D28 (-3/+7)	D56 (+7)
In person visit	Х	Х	
Digital Questionnaire			Х
Consent	Х	Х	
Randomisation	Х		
Vaccination with LAIV	Х		
Placebo nasal spray		Х	
Collection of SAEs, and	To b	pe reported at any time up	to D56
MAAEs			
	Late Vacc	ine Group	
	D0	D28 (-3/+7)	D56 (+7)
In person visit	Х	Х	
Digital Questionnaire			Х
Consent	Х	Х	
Randomisation	Х		
Vaccination with LAIV		Х	
Placebo nasal spray	Х		
Collection of SAEs, and MAAEs	To b	pe reported at any time up	to D56

This trial is being conducted with a company called uMed, a clinical research technology platform, who partners with UK Healthcare Providers to access NHS Electronic Health Record (EHR) data and invite patients to participate in research. uMed has been engaged by the Sponsor to identify, contact, and obtain consent from prospective patients. uMed will collect study outcomes, thereby diminishing the administrative workload of clinical staff, and capture other relevant protocol data. uMed will also support site contracting and setup.

## 4 Lay Summary

The virus that causes influenza (flu) is a common cause of minor illness but is also one of the most important causes of serious lung infections. The people most at risk of serious illness are the elderly, those with weakened immune systems, and very young children. Whilst most children do not suffer from serious illness, young children with flu also spread the virus easily in the wider population, increasing illness in the elderly.

There are vaccines available which can help protect people from developing serious illness from influenza and may also prevent some transmission of the virus. These vaccines are offered to elderly and vulnerable people every autumn in the UK in the form of an injection, as well as to children over the age of two years in the form of a nasal spray. This spray contains a live, but weakened form of the influenza virus which has been modified so it cannot grow in warm conditions, such as in the lungs.

The nasal spray vaccine is a live version of flu that has had the dangerous flu proteins removed (called "attenuation"), so it causes immunity from flu but not serious influenza illness. The vaccine has also been modified to be "cold adapted", meaning that it can only live in the colder nasal passages in the nose and will not survive if it is inhaled into the lungs. In the UK specialists consider it is safe to the nasal spray vaccine to be given to children 2 years and older with asthma or more serious lung conditions such as cystic fibrosis, to avoid having to use an injection vaccine.

Children less than two years currently cannot receive the nasal spray vaccine. This is because during the original studies of this vaccine, there was not enough evidence to demonstrate that it did not cause wheezing illness in children of this age. Wheezing is a whistling noise in the lungs which suggests that the tubes in the airways are more narrow than usual. Wheezing is commonly seen in older children and adults with asthma, and in younger children with many different respiratory viruses. It could also occur if the airways react to the virus in the vaccine. More evidence is required to demonstrate whether the vaccine is safe enough that we could offer it to children less than two years of age to protect them against serious illness from influenza and prevent spread of the virus from this age group to other, more vulnerable people.

All children in the FluSNIFF-toddler trial will receive the nasal flu vaccine. At the start, 1500 children aged 12 to 23 months will be given the nasal spray influenza vaccine (Fluenz), and 1500 children will receive nasal spray of a placebo. We will then compare how many children in each group were brought to see a doctor who diagnosed wheezing in their chest in the following four weeks. Then, four weeks later, the children will return for their second study visit. If they had LAIV at the first visit, children will

receive the placebo, and if they originally received the placebo children will then receive LAIV. We will again compare rate of wheezing in each group over the following four weeks.

The children's parents will not know whether their child received the vaccine or the placebo, so that this does not influence how likely they will be to visit their doctor.

If there are similar amounts of wheezing detected by doctors in children who have had the LAIV vaccine or the placebo, then then the UK may be able to offer the vaccine to children aged one year and over in the future. As for all vaccines, this decision will be made for the NHS by the Government's Joint Committee of Vaccination and Immunisation.

## 5 Background

Influenza is a significant public health concern globally, with substantial morbidity and mortality rates, especially in vulnerable populations such as children. In the paediatric population, influenza is associated with a high rate of hospital admissions, particularly among young children and those with underlying health conditions. Influenza can lead to severe respiratory illnesses, including pneumonia, and exacerbate existing medical conditions. Children are thought to make a significant contribution to the broader spread of influenza, including to more vulnerable populations (1).

In the United Kingdom, the burden of influenza among children is notable, with considerable implications for paediatric healthcare services and broader public health. Seasonal influenza epidemics result in significant numbers of paediatric hospitalisations and GP consultations each year. The impact extends beyond immediate health concerns, affecting school attendance, parental employment, and the overall well-being of families.

The vaccination program against influenza in the UK aims to reduce this burden by providing immunity to those most at risk and curbing the transmission of the virus within the community. Vaccination is recognized as the most effective method of preventing influenza and its associated complications. The national vaccination program has historically targeted groups considered at high risk, including older adults, individuals with chronic health conditions, healthcare workers, and children from age 2 upwards with the nasal flu vaccine from 2013 (2, 3).

The rationale for extending the vaccination program to children, particularly those under five years of age, is twofold. First, this age group is at a higher risk of influenza-related complications and hospitalizations. Second, vaccinating children can contribute to herd immunity, thereby reducing transmission rates within the community and protecting vulnerable populations that are less responsive to the vaccine, such as the elderly and immunocompromised individuals.

# 6 Study Rationale

The UK Joint Committee on Vaccination and Immunisation (JCVI) have asked the National Immunisation Schedule Evaluation Consortium (NISEC) to undertake a clinical trial of LAIV in children aged 12 - 23 months, investigating only safety outcomes (no blood tests in the main trial cohort), to inform JCVI decision making for the 2026-7 winter influenza season. A new trial focussing on specific safety outcomes in children 12-23 months old is needed as the initial phase 3 trial leading to licensure suggested a possible increased incidence of wheezing post-vaccination in this age group (4). As a result, the vaccine is not currently approved for children under 2 years old. Given the potential

benefits of expanding the vaccination coverage, this study aims to assess the safety profile of LAIV in 1-2-year-old children, addressing the gap in evidence and contributing to informed decision-making regarding vaccine policy and implementation.

# 7 Synopsis

Trial Title  A phase 2 randomised, single blinded, placebo controlled, cross-over trial of a single attenuated influenza vaccine (FluSNIFF-toddler)			trial of a single dose of live		
Internal ref. no. (or short title)	LAIV safety in 12-23 month old children (FluSNIFF-toddler)				
Trial registration	ISRCTN: xxxx				
Sponsor	University Hospital Southampton NHS Foundation Trust  [name]  [name]				
Funder	National Institute for Health and Care Research via NIHR204677 National Immunisation Schedule Evaluation Consortium (NISEC) II				
Clinical Phase	nical Phase 2				
Trial Design	Randomised, single blinded, placebo controlled, cross-over, trial of live, attenuated influenza vaccine in children aged 12 – 23 months				
Trial Participants	Children aged 12 months to 23 months (up to one day before their second birthday) in good health				
Sample Size	3000 children				
Planned Trial Period	56 days per participant (following on following on follow	, , , , , , , , , , , , , , , , , , ,			
	Objectives	Outcome Measures	Timepoint(s)		
Primary	To determine the safety and reactogenicity of LAIV in children	Episode of respiratory wheeze diagnosed by a health practitioner	Day 0 to 28 following vaccination		

			requiring medical attention		
	To assess safety of LAIV		Serious adverse events	Throughout the study	
Key secondary			All medically attended adverse events	Throughout the study	
		Vaccine	Dose	Route of administration	
Intervention(s)  • IMP(s)		Fluenz nasal spray	10  FFU of:  A/Victoria/4897/2022, A/Thailand/8/2022, B/Austria/1359417/2021  (0.2ml)	Intranasal	
		0.9% Saline placebo nasal spray	0.2ml	Intranasal	

## 8 Risks and Benefits

## 8.1 Potential benefits

Participants in the study will receive a vaccine against seasonal influenza which otherwise will not be available to them through the national immunisation programme. Receipt of the vaccine may provide immune protection against the circulating strains of influenza during this autumn/winter season.

#### 8.2 Potential risks

### 8.2.1 Allergic reactions

Allergic reactions from mild to severe may occur in response to any constituent of a medicinal product's preparation. Anaphylaxis or other hypersensitivity disorders are known to occur in between 1/1000 and 1/100 recipients of LAIV.

(https://www.medicines.org.uk/emc/product/3296/smpc#about-medicine)

## 8.3 Reactogenicity

More than 1 in 10 people may experience nasal congestion or discharge, reduced appetite or weakness, and up to 1 in 10 people may experience fever, muscle aches or headaches following vaccination with LAIV. The investigation of lower respiratory tract reactogenicity outcomes is the primary reason for this trial.

## 9 Objectives and Outcome Measures

Objectives	Outcome Measures	Timepoint(s)			
Primary					
To determine the safety and reactogenicity of LAIV in children	Episode of respiratory wheeze requiring medical attention diagnosed by a health practitioner	Day 0 to 28 following vaccination			
	Key secondary				
To assess safety of LAIV	Serious adverse events	Throughout the study			
	All medically attended adverse events	Throughout the study			

## 9.1 Outcome ascertainment

Outcomes will be collected from routine GP medical records by the digital CRO, uMed. For medically attended wheeze, specific codes referring to a diagnosis of "Viral induced wheeze" and "Asthma" will be used, alongside findings of "Wheeze", and any new prescription for either Salbutamol or Ipratropium Bromide:

- 276191000000107 | Viral wheeze (disorder)
- 195967001 | Asthma (disorder)
- 56018004 | Wheezing (finding)
- 24612001 | Wheeze rhonchi (finding)
- 372897005 | Salbutamol (substance)
- 372518007 | Ipratropium (substance)

Whilst using codes of a finding of "wheeze" are most specific to the primary outcome, these codes are rarely used in practice and yield insufficient events. GP EPR data from a 3 month period indicates that, "Viral induced wheeze", and "Asthma" are the codes most commonly associated with wheezing. This

yields a population incidence of roughly 2% during a three-month period, in line with the power calculations for the study.

The primary outcome includes all events coded with a finding of "wheeze" together with the addition codes asthma/viral wheeze/salbutamol/ipratropium.

Additional medical attendances at locations other than the child's primary GP practice (e.g., hospital or other GP locations) will be determined using electronic diaries and solicited at follow up visits.

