#### 15 Statistics

#### 15.1 Sample size

The primary objective of this study is to determine the relative risk of medially attended wheezing in 28 days following LAIV vaccination compared with placebo. The null and alternate hypotheses are:

H0: Proportion of wheezing LAIV = Proportion of wheezing Placebo

H1: Proportion of wheezing LAIV ≠ Proportion of wheezing Placebo

Where the proportion of wheezing is calculated as the number of participants with respiratory wheezing diagnosed by a health practitioner requiring medical attention within 28 days following receiving LAIV or a placebo. We chose 28 days as this is the common interval to observe intermediate reactions following vaccination. The study was a cross-over design, i.e. participants randomised to LAIV or placebo at Day0 will receive placebo or LAIV at Day28, respectively. Although there is no data on the ideal washout period, it is biologically reasonable to assume that the impact of LAIV will last shorter than 28 days. The data from a previous publication comparing medically significant wheeze rates between LAIV and inactivated vaccine groups reported 44 vs 20 cases in the first 28 days following vaccination, and 11 vs 14 cases between 29-42 days post-vaccination, further supporting our assumption. Therefore, we will use both Day 0-28 and Day 28-56 periods in the primary analysis in the primary analysis.

The sample size calculation is based on the below assumptions:

- 1. The proportion of medially attended wheezing is 0.9% following placebo in 28 days following vaccination;
- 2. The relative risk of interest is 2;

- 3. Study power of 80%;
- 4. Type I error of 0.05 two-sided;

Based on the above sample size, the study will need to recruit 2800 effective participants. Given the study endpoint will be extracted based on electronic medical records, we expect the attrition rate will be low. The total sample size will be 3000.

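### The GP-record incidence of about 2% in three months is about 0.61% per 28 days, so it does not support the 0.9% assumed in the power calculation as section 9.1 says

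*Protocol*

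**What the plan says.** Protocol section 15.1 sizes the trial on four inputs: "The proportion of medially attended wheezing is 0.9% following placebo in 28 days following vaccination"; "The relative risk of interest is 2"; power of 80%; and "Type I error of 0.05 two-sided". It concludes that "the study will need to recruit 2800 effective participants" and, after an allowance for attrition, "The total sample size will be 3000". Both 28-day periods enter the primary analysis, and section 15.2 compares them with Pearson's chi-squared test on the combined data.

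Section 9.1 defines how the outcome is found in GP records and gives a figure from three months of GP data. It says that this "yields a population incidence of roughly 2% during a three-month period, in line with the power calculations for the study". The protocol does not convert the three-month figure to 28 days, and section 15.1 gives no source for 0.9%.

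Sections 3, 11.1 and 12.1.1 say that recruitment is enriched for children at higher risk of wheeze. No target proportion or expected rate is stated.

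**The concern.** Section 9.1 offers the GP-record figure as empirical support for the power calculation, and it is the only such support that the protocol shows for 0.9%. On a common time base the two figures differ by a factor of about 1.5, so the support is not there as stated.

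This matters because of how the result will be read. The trial tests for a difference against a null of equal proportions. The lay summary (section 4) says that similar amounts of wheeze in the two groups may allow the vaccine to be offered from one year of age. A non-significant result would therefore be taken as reassurance, and its value depends on the chance that a true doubling would have been detected. If the placebo rate were the cited population rate, that chance would be clearly below the stated 80%.

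**Working it through.** **Inputs.** Placebo 0.9% in 28 days, relative risk 2, power 80%, two-sided 0.05, 2800 effective and 3000 total (section 15.1). Population incidence 2% in three months (section 9.1). Assumption: three months = 91.3 days. Each child contributes one LAIV and one placebo period, so 2800 children give 2800 observations per product.

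**Step 1: reproduce 2800.** With p1 = 0.009, p2 = 0.018, d = 0.009 and mean p = 0.0135:

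n = [1.960 × √(2 × 0.0135 × 0.9865) + 0.842 × √(0.009 × 0.991 + 0.018 × 0.982)]² / d² = (0.3199 + 0.1373)² / 0.000081 ≈ 2580.

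With continuity correction: n × [1 + √(1 + 4/(n × d))]² / 4 = 2580 × (1 + 1.0827)² / 4 ≈ 2798.

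This matches the stated 2800. Reading 2800 as 1400 per arm gives only 54% power, so the cross-over reading is the one intended.

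**Step 2: common time base.**
- 2% × 28/91.3 = 0.613% per 28 days. At constant hazard, 1 − 0.98^(28/91.3) = 0.618%. Plain division by three gives 0.67%.
- 0.9% × 91.3/28 = 2.93% in three months (2.90% at constant hazard).
- Ratio: 0.9/0.613 = 1.47.

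**Step 3: power at relative risk 2, changing only the placebo rate.** Power = Φ{[d√n − 1.960 × √(2 × mean p × (1 − mean p))] / √(p1(1 − p1) + p2(1 − p2))}. The continuity-corrected version subtracts 1/√n from d√n.

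For 0.613% against 1.227% with n = 2800: d√n = 0.3246, the null term is 0.2646 and the denominator is 0.1350. Uncorrected: (0.3246 − 0.2646)/0.1350 = 0.444, power 67%. Corrected: (0.3246 − 0.0189 − 0.2646)/0.1350 = 0.304, power 62%.

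| Placebo rate, 28 days | n | Uncorrected | Continuity-corrected |
|---|---|---|---|
| 0.90% | 2800 | 83% | 80% |
| 0.75% | 2800 | 76% | 72% |
| 0.67% | 2800 | 71% | 66% |
| 0.61% | 2800 | 67% | 62% |
| 0.61% | 3000 | 70% | 65% |

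At 0.61% and n = 2800, a McNemar calculation with independent periods gives 67% and Fisher's exact test 63%.

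**Step 4: expected events, placebo against LAIV, n = 2800.** At 0.9%: 2800 × 0.009 = 25 against 50. At 0.613%: 17 against 34.

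**Step 5: rounding of the 2%.** Taking 1.5% to 2.5% as an assumed range gives 0.46% to 0.77% per 28 days. Power at 2800 then runs from 48–55% to 73–77%. None of these reaches 80%.

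**The case against.** The strongest reply is that the sample-size calculation contains no error. Section 15.1 sets 0.9% as a planning assumption and does not derive it from section 9.1, and 2800 follows from it. This stands. A reader might infer that the sample size is miscalculated, or that the trial's power simply is 62–67%. The documents support neither. The lower figure needs the trial's placebo rate to equal the GP population rate.

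There are good reasons why it might not:
- The 2% most naturally refers to the viral wheeze and asthma codes in GP records. The endpoint also counts wheeze findings, new salbutamol or ipratropium prescriptions, and attendances outside the child's own practice.
- Recruitment is enriched, while the 2% is a population figure.
- The season of the GP data is not given, and the trial runs in autumn and winter.
- If 2% is the share of children with at least one event, 0.61% is a lower bound for the average 28-day share, because a child can wheeze in more than one window.

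Together these could supply a factor of about 1.5; two uplifts of 21% each would do so (1.21 × 1.21 = 1.46; illustrative). But the protocol quantifies none of them and does not give any of them as the reason for 0.9%. Section 9.1 claims agreement for the population figure itself.

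It is also fair that section 15.2 names Pearson's test without a correction, so 67% against 83% is the comparison for that test. The 62% against 80% is the like-for-like comparison with the formula that reproduces 2800. Finally, the confidence intervals planned in section 15.2 will show the precision actually achieved, which limits the harm from an optimistic planning rate.

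**Conclusion.** The statement of agreement in section 9.1 is wrong on the protocol's own figures: 0.61% against 0.9% per 28 days, a gap of about 1.5-fold. That holds whichever formula is used and does not depend on what rate the trial observes.

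The consequence for power is conditional. If the placebo rate equals the cited population figure, the chance of missing a true doubling is 33–38% with 2800 effective participants (30–35% with all 3000), against the planned 20%. If enrichment, wider ascertainment and season bring the rate to 0.9%, the stated 80% is right. The protocol gives no figure with which to choose between these cases. Severity is moderate: it should be fixed, but it invalidates neither the design nor the calculation.

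**What to change.** In section 9.1, remove the statement of agreement, or replace it with the 28-day equivalent (about 0.61%) and an explanation of why a higher rate is expected in the trial.

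In section 15.1, do one of two things:
- justify 0.9% by stating the combined uplift of about 1.5 times expected from enrichment, wider ascertainment and season, with its basis; or
- restate power at relative risk 2 for 28-day placebo rates from about 0.6% (62–67%) to 0.9% (80–83%), saying whether a continuity correction is used.

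Section 14.11 uses the same 0.9% for the safety board's power statement and should be kept consistent with whatever is decided.

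The cost is rewording. If the second route is taken, the stated power becomes less favourable. No change in sample size, endpoint or analysis is proposed.
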